Objectives: Describe the demographics, laboratory values, and secondary hyperparathyroidism (SHPT) medication use (specifically cinacalcet), and the occurrence of hypocalcemia, seizures, and infections (requiring hospitalization), in cinacalcet treated and untreated patients enrolled in the North American Pediatric Renal Trials and Collaborative Studies (NAPRTCS) receiving dialysis for chronic kidney disease (CKD).

Hypotheses: Patient characteristics, overall and for cinacalcet treated and untreated patients, will be described; the rate of hypocalcemia, seizure, and infection (requiring hospitalization) events will be estimated separately in cinacalcet treated and untreated patients enrolled in NAPRTCS.

Variables of Interest: Parameters of interest include: Age, height, dry weight, Tanner stage, sex, race, cinacalcet use (yes/no), cinacalcet start/stop dates, cinacalcet dose (mg), parathyroid hormone (PTH) (pg/mL), corrected calcium (mg/dL), phosphorus (mg/dL), phosphate binder use (yes/no), vitamin D sterol use (yes/no), hypocalcemia (yes/no), seizures (yes/no), and infections requiring hospitalization (yes/no).

Study Design: The NAPRTCS registry is a prospective, observational study of patients with CKD. This protocol will collect and tabulate a specific set of information from the NAPRTCS registry. Specifically, dialysis registry patients will be included and followed for up to three years, or for six semiannual data collection intervals. Patients will be censored at three years, transplant, death, loss to follow-up, or if no longer participating in NAPRTCS, whichever occurs first.

Sample Size: Estimated to be approximately between 1000 to 1500 patients over 3 years

Summary of Patient Eligibility Criteria: All pediatric patients < 21 years old receiving maintenance dialysis (hemodialysis or peritoneal dialysis) at a NAPRTCS affiliated center are eligible. Patients who are participating in an Amgen clinical study are ineligible. For a full list of eligibility criteria, please refer to [Section 4.4](#).

[figure not shown]
Procedures: In this prospective, observational, noninterventional registry, physicians will continue to treat their pediatric dialysis patients as per standard medical care. There are no specific study procedures required by this protocol.

Statistical Considerations: This protocol specifies descriptive statistics that will be completed by NAPRTCS. No hypotheses will be tested or implied by the produced reports. For a full description of statistical analysis methods, please refer to [Section 13](#).

Sponsor: Amgen Inc.

Approved

Study Schema

Note: Patients will be followed from study start until death, transplant, withdrawal, transfer to a nonparticipating facility, or the end of the study period

Approved

Study Glossary

Abbreviation or Term	Definition/Explanation
AESI	Adverse Event of Special Interest
CKD	Chronic Kidney Dialysis
eGRF	Estimated Glomerular Filtration Rate
ESRD	End Stage Renal Disease
FDA	Food and Drug Administration
HD	Hemodialysis
HPT	Hyperparathyroidism
IEC	Independent Ethics Committee
IRB	Institutional Review Board
NAPRTCS	North American Pediatric Renal Trials and Collaborative Studies
NKF KDOQI	National Kidney Foundation – Kidney Disease Outcomes Quality Initiative™
PD	Peritoneal Dialysis
PTH	Parathyroid Hormone
SHPT	Secondary Hyperparathyroidism
USRDS	United States Renal Data Systems

Approved

TABLE OF CONTENTS

	Page
Protocol Synopsis.....	3
Study Schema.....	4
Study Glossary.....	5
1. INTRODUCTION.....	8
2. OBJECTIVES.....	8
3. BACKGROUND AND RATIONALE.....	8
3.1 Rationale for the Study.....	9
3.2 Adverse Events of Special Interest.....	9
3.3 Study Hypotheses.....	9
4. STUDY PLAN.....	10
4.1 Study Design.....	10
4.2 Number of Sites.....	10
4.3 Description of Data Source.....	10
4.4 Summary of Patient Eligibility Criteria.....	10
4.5 Study Period and Follow-up.....	11
5. PATIENT ENROLLMENT.....	11
6. DATA COLLECTION PROCEDURES.....	11
7. DEFINITION OF EXPOSURE, OUTCOME, AND OTHER STUDY VARIABLES.....	11
7.1 Exposure.....	11
7.2 Variables of Interest.....	11
7.3 Other Study Variables.....	12
8. TIME AT RISK FROM EXPOSURE.....	12
9. POTENTIAL SOURCES OF BIAS IN STUDY.....	12
9.1 Confounding by Indication and Information Bias.....	12
9.2 Ascertainment of Adverse Events of Special Interest Bias.....	13
10. REMOVAL AND REPLACEMENT OF SUBJECTS.....	13
11. SAFETY DATA COLLECTION, RECORDING, AND REPORTING.....	13
12. SAMPLE SIZE CONSIDERATIONS.....	14
13. STATISTICAL ANALYSIS.....	14
13.1 Data Collection and Management.....	14
13.1.1 Descriptive Analyses.....	14

Approved

13.1.2	Analyses.....	15
13.2	Planned Methods of Analysis	15
13.3	Missing Data and Loss to Follow-up.....	15
13.4	Annual Analysis.....	15
13.5	Final Analysis.....	16
14.	STRENGTHS AND LIMITATIONS.....	16

1. INTRODUCTION

The purpose of this protocol is to detail the rationale, objectives, data source, and methods, along with limitations, of a planned report describing patient characteristics and safety events among real-world-treated pediatric patients receiving dialysis for chronic kidney disease (CKD) in North America, who are participants in the ongoing North American Pediatric Renal Trials and Collaborative Studies (NAPRTCS) pediatric kidney disease registry (<https://web.emmes.com/study/ped/>).

2. OBJECTIVES

Specific objectives of this study are to tabulate and report the listed characteristics and events for subjects with data in the NAPRTCS registry who have end stage renal disease (ESRD), who are managed in medical practice with or without cinacalcet treatment. The following data characteristics and events are of interest:

- demographic characteristics
- laboratory values
- secondary hyperparathyroidism (SHPT) medication use
- occurrence of hypocalcemia
- occurrence of seizures
- occurrence of infections requiring hospitalization

3. BACKGROUND AND RATIONALE

CKD in children, as in adults, is a devastating illness. The mortality rate in children receiving dialysis is 30 to 150 times greater than that of the general pediatric population ([U.S. Renal Data System, USRDS 2006 Annual Data Report; McDonald and Craig, 2004](#)).

As in adults, pediatric patients on dialysis often have SHPT associated with substantial elevations of parathyroid hormone (PTH) as well as dysregulation of calcium and phosphorus metabolism. SHPT can lead to the development of high-turnover bone disease, and the resultant changes in structural bone integrity may lead to an increased risk of deformities and fractures in children on dialysis ([Cundy et al, 1985; Spasovski et al, 2003; Coen et al, 1996; Sanchez, 2003; Salusky et al, 1987; Slatopolsky et al, 1999](#)). SHPT is also felt to play a role in growth retardation in children potentially through

Approved

alterations in bone architecture (including lesions in the epiphyseal growth plate), which interfere with bone formation and lead to impaired bone growth (Kuizon and Salusky, 1999). Additionally, studies have shown that young adults with ESRD and childhood-onset CKD also display a high incidence of cardiovascular complications (Cheung et al, 2000; Oh et al, 2002), which may be in part attributable to SHPT.

Phosphate binders and vitamin D sterols are indicated for use in pediatric patients with ESRD, however there remains a significant unmet need for additional therapies for SHPT. A recent survey conducted among 18 sites belonging to NAPRTCS (NAPRTCS, unpublished data) included 320 pediatric hemodialysis (HD) and peritoneal dialysis (PD) patients between the ages of 2 to less than 18 years. Results of the survey show that overall, 53% of the pediatric dialysis population have PTH levels above 300 pg/mL, which was the upper limit recommended by the NKF KDOQI™ guidelines for all pediatric age groups (NKF KDOQI™ 2004) at the time of the survey.

3.1 Rationale for the Study

The purpose of this study is to collect data to inform on the use of cinacalcet in pediatric patients receiving dialysis in clinical practice. No comparisons will be made due to potential confounding by indication, in which patients who receive cinacalcet are different with respect to risk factors for adverse events of special interest (AESI), which is likely to bias any comparison between cinacalcet use groups.

This study will generate a report specifically looking at the AESI in pediatric patients treated with or without cinacalcet in a real-world setting.

3.2 Adverse Events of Special Interest

In response to a specific regulatory request, hypocalcemia, seizures, and infections requiring hospitalization are being collected as AESI. Hypocalcemia and seizures have been identified in prior clinical trials in adults and are listed in the product label for cinacalcet. Infections are a common occurrence in pediatric patients on hemodialysis and peritoneal dialysis.

3.3 Study Hypotheses

Patient demographics overall and for cinacalcet treated and untreated patients will be described, and the rate of hypocalcemia, seizure, and infection (requiring hospitalization) events, will be estimated separately in cinacalcet treated and untreated patients enrolled in the pediatric dialysis registry.

Approved

4. STUDY PLAN

4.1 Study Design

This is a prospective, observational study with semiannual data collection and reporting of descriptive findings. The single data source will be the NAPRTCS registry.

4.2 Number of Sites

Approximately 130 sites in the United States, Canada, Mexico, and Costa Rica currently contribute data to the NAPRTCS registry.

4.3 Description of Data Source

NAPRTCS is a voluntary registry of pediatric patients who have chronic kidney disease and who are receiving dialysis, and who are receiving care in approximately 130 pediatric nephrology centers in the United States, Canada, Mexico, and Costa Rica. Aside from the participating centers, the registry consists of a Clinical Coordinating Center and a Data Coordinating Center. Patients are eligible for inclusion if they are < 21 years of age, and are being treated for chronic renal insufficiency or ESRD at a participating center. Patients are treated according to local standards of care. Upon inclusion in the registry, patient data are collected via an electronic data capture form, which is completed by each center on a voluntary basis. For dialysis patients, baseline data (within 30 days of dialysis start) are collected, including predialysis serum creatinine concentration, and length/height (used to derive estimated glomerular filtration rate (eGFR) in mL/min/1.73 m² via Schwartz's method). Data currently collected by NAPRTCS include demographic and clinical characteristics, select laboratory, hospitalization, and medication variables. Data also include transplant evaluation, access revisions, dialysis modality termination, transplant and vital status. After the baseline assessment, data on these parameters are collected every six months.

Since its beginning in 01 January 1992, the registry has included data from approximately 7000 pediatric dialysis patients. Data from approximately 300 patients are expected in every 6-month interval assessment.

4.4 Summary of Patient Eligibility Criteria

Tabulations will include all patients < 21 years of age receiving maintenance dialysis at a NAPRTCS affiliated center, and who are enrolled in the registry. The tabulation analyses will be repeated to include only those patients < 18 years of age.

Patients who are currently enrolled in an Amgen clinical trial will not be included.

Approved

4.5 Study Period and Follow-up

Data to be included in the report will be from a time period of approximately 3 years, from July 2012 to July 2015.

The start of time at risk (index date) will begin at the time of each eligible patient's entry into the NAPRTCS registry.

Patients will be followed from study start until death, transplant, withdrawal, transfer to a nonparticipating facility, or end of the study period.

The primary completion date is defined as 01 July 2015.

5. PATIENT ENROLLMENT

All patients who meet entry criteria and who contribute data to the NAPRTCS registry during the time period of this study will be enrolled and included in the report.

6. DATA COLLECTION PROCEDURES

Data used to generate the reports for this study will be collected by the NAPRTCS registry, and that data will remain with NAPRTCS. NAPRTCS will generate all reports.

No data, nor datasets of any type, will be available from NAPRTCS to Amgen as part of this study.

7. DEFINITION OF EXPOSURE, OUTCOME, AND OTHER STUDY VARIABLES

7.1 Exposure

The exposure is defined as cinacalcet therapy. Patients are considered exposed for the duration from start to stop date of receiving cinacalcet, and for 7 days afterwards.

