13.1.1 Descriptive Analyses

Since the study is descriptive in nature, the analyses will describe the study population and outcomes in all study cohorts, for age < 21 years, for age < 18 years, as well as in different follow-up time periods (before and after cinacalcet exposure). This will include the following:

Approved

- total number of patients and total number of patient-years observation based on the annual data reporting periods, and for the cumulative 3-year study period
- estimation of rates of cinacalcet use based on the annual data reporting periods, and for the cumulative 3-year study period
- estimation of rates of AESI based on the annual data reporting periods, and for the cumulative 3-year study period
- proportion of patients who received at least 1 dose of cinacalcet within 7 days preceding an episode of hypocalcemia (from amongst all patients who developed hypocalcemia)

In addition, the following descriptive analyses using summary statistics will also be conducted:

- a tabular summary (eg, frequency, percent, rate) of categorical baseline demographic and clinical characteristics by cinacalcet-exposed and cinacalcet-unexposed
- for continuous variables (eg, age, weight, laboratory values) summary statistics for measures of central tendency (mean, median, SD, Q1, Q3, min, max) will be provided by cinacalcet-exposed and cinacalcet-unexposed

The cinacalcet utilization pattern will also be assessed (eg, dosing, duration of treatment).

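### On-drug event rates pool patients already taking cinacalcet when follow-up opens with patients who start it during the study, and no planned table separates them

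*Protocol*

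**What the plan says.** Section 5 defines the cohort: "All patients who meet entry criteria and who contribute data to the NAPRTCS registry during the time period of this study will be enrolled". Section 4.4 adds no condition on past or current cinacalcet use. It says "Tabulations will include all patients < 21 years of age receiving maintenance dialysis at a NAPRTCS affiliated center", and its one exclusion is "Patients who are currently enrolled in an Amgen clinical trial will not be included". The registry dates from 1992 (Section 4.3), whereas for the report Section 4.5 states "Data to be included in the report will be from a time period of approximately 3 years, from July 2012 to July 2015". Children already on the drug in July 2012 are therefore included.

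Section 4.5 describes the start of follow-up in two ways: "The start of time at risk (index date) will begin at the time of each eligible patient's entry into the NAPRTCS registry" and "Patients will be followed from study start until death, transplant, withdrawal, transfer to a nonparticipating facility, or end of the study period". Neither refers to the first dose.

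Exposed time is a single state under Section 7.1: "Patients are considered exposed for the duration from start to stop date of receiving cinacalcet, and for 7 days afterwards". Section 9.1 adds that the summary table counts any use as exposed, with events linked to treatment windows.

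Among the analyses in Section 13.1.1 is "estimation of rates of AESI based on the annual data reporting periods, and for the cumulative 3-year study period". That section also plans results for ages under 21 and under 18, results before and after cinacalcet exposure, and a description of treatment duration. None of these divides on-drug time by time since first start, or starters from continuing users. Section 13.4 confines the annual analysis to what Section 13 describes. The biases in Section 9 and the limitations in Section 14 do not mention patients already on the drug.

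**The concern.** A child who began cinacalcet well before July 2012 and a child who begins in 2013 add the same kind of exposed time. The first child's initiation period lies outside the data window. That child's exposed time enters only because treatment was still running, so it may over-represent children who tolerate the drug. The before/after split does not help, because a continuing user may have no time before exposure inside the window.

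Section 3.2 says the events are collected in response to a regulatory request. A reader of the report may well take the on-drug rate as what to expect when a child is started on cinacalcet. If hypocalcemia or seizures cluster soon after starting, the pooled rate understates that risk, and nothing in the planned tables would show it.

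**Working it through.** **The plan's own figures.** Table 1 in Section 12 uses the half-width 1.96 × √(p(1 − p)/N). All eight cells reproduce to three decimals; for example, N = 300 and p = 0.01 give 0.01126, against 0.011 in the table. Nothing in Table 1 is in dispute. It is used below only to price the fix.

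**Inputs from the protocol.** About 300 patients per 6-month interval (Section 4.3), six intervals (Synopsis), 1000 to 1500 patients in total, and 200 to 300 likely to receive cinacalcet (Section 12).

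**Inputs the protocol does not give.** The share p of treated patients already on drug when follow-up opens, and the ratio k of the event rate in the first six months to the later rate. Both are assumed here.

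**A rough guide to p.** If the first interval holds about 300 patients, then 300/1500 = 20% to 300/1000 = 30% of the cohort is present at opening. With equal cinacalcet use across patients, the same share of users was present. Some of them would start later, which lowers p. If longer-dialysed children use the drug more, p is higher. I take 20% to 50%.

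**Main model.** Each treated patient contributes one on-drug year, and continuing users are all past six months. Setting the later rate to 1:

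- starters' first-year rate = (k + 1)/2
- pooled rate = p × 1 + (1 − p) × (k + 1)/2
- shortfall relative to starters = p(k − 1)/(k + 1)

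| k | p | Pooled | Starters | Shortfall |
|---|---|---|---|---|
| 1 | any | 1.00 | 1.00 | 0% |
| 2 | 0.2 | 1.40 | 1.50 | 7% |
| 2 | 0.3 | 1.35 | 1.50 | 10% |
| 2 | 0.5 | 1.25 | 1.50 | 17% |
| 3 | 0.2 | 1.80 | 2.00 | 10% |
| 3 | 0.3 | 1.70 | 2.00 | 15% |
| 3 | 0.5 | 1.50 | 2.00 | 25% |

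**Sensitivity to time on drug.** Six intervals × 300 patients × 0.5 year = 900 patient-years, or 0.6 to 0.9 years per patient for 1500 to 1000 patients. One on-drug year each is therefore generous. With 9 on-drug months per patient, a rate ratio of 2 to 3 and 25% to 50% already on drug:

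- a 6-month early period gives pooled/starter ratios of 0.90 to 0.71 (10% to 29% low)
- a 3-month early period gives 0.94 to 0.80 (6% to 20% low)

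The order of magnitude does not change.

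**Precision after separation.** Of 300 users, p = 0.2 leaves 240 starters and p = 0.5 leaves 150. At an event probability of 0.01 the half-width rises from 0.0113 to 0.0126 and 0.0159; at 0.05 it rises from 0.0247 to 0.0276 and 0.0349.

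**The case against.** The study is descriptive, and Section 3.1 rules out comparisons. A rate over all on-drug time is a valid description of children currently taking the drug, and the protocol does not claim to estimate a rate in starters. This stands, and it is why the pooled rate should be kept and labelled. It does not settle the matter, because the difficulty is what the single on-drug rate means, whether or not it is compared with anything.

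It can also be said that extra table columns belong in a statistical analysis plan that is not shown. But the entry and exposure rules are fixed in the protocol, and Section 13.4 limits the annual analysis to Section 13, so the split cannot be presumed to exist elsewhere.

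The strongest objection is sparse data. Section 12 puts the background rate of hypocalcemia and seizures below 1%. At 1%, 300 users give about 3 events, with an exact Poisson 95% interval of about 0.6 to 8.8, which is far wider than a shift of 7% to 25%. Section 14 already concedes low counts. This limits what the split can show for rare events and argues against splitting within each year and age group. It has less force for infections, which Section 12 expects to be more common.

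Three stronger readings go beyond the documents:

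- A reader might infer that annual rates would fall as long-term users accumulate. The registry is open: if about 300 patients are present in the first interval, (1000 − 300)/5 = 140 to (1500 − 300)/5 = 240 new patients enter in each later one. The mix may shift in either direction.
- A reader might set the pooled rate against the starters' first six months (1.5 against 3.0 at k = 3, p = 0.5) and call it half. Of that gap of 1.5, 1.0 comes from averaging starters over a full year (3.0 to 2.0) and only 0.5 from pooling.
- A reader might infer that children who stopped early vanish from the study. They remain, as unexposed patients. Only the exposed time is selected.

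**Conclusion.** The structural point holds. Sections 5, 7.1 and 13.1.1 together put on-drug time from continuing users and from starters into one rate, and none of the planned splits separates them. Whether this distorts anything depends on risk being higher early in treatment, which the documents neither state nor rule out.

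Under the main model's assumptions, the pooled rate is roughly 7% to 25% below the starters' first-year rate. These figures are illustrations, not estimates. The problem lies mainly with patients in the registry before July 2012: registry baseline falls within 30 days of dialysis start (Section 4.3), so new entrants should include fewer established users. This is a worthwhile and inexpensive improvement to how the rate can be read. It does not invalidate the study.

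**What to change.** In Section 13.1.1, use the start dates already listed in Section 7.2 to report, for the cumulative 3-year period, event counts, patient-years and rates:

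- separately for patients who start cinacalcet on or after the start of follow-up and for those already on it at that point
- by time since first start, for example the first 6 months and later, which matches the semiannual interval

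State in advance where a patient who restarts after an earlier course is counted. Reconcile the two statements in Section 4.5 on when follow-up begins, since the classification depends on that date.

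Keep the pooled rate and label it as describing current users. Name use that precedes follow-up as a source of bias in Section 9 and as a limitation in Section 14.

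The cost is one classification of existing dates and a few table columns, with no new data collection. The downside is smaller cells and wider intervals, especially for hypocalcemia and seizures, so the split should be confined to the cumulative report.

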7.2 Variables of Interest

Variables of interest for this study are as follows:

- cinacalcet prescription start and stop dates
- dose of cinacalcet (mg)
- occurrence and date of seizures
- occurrence and date of infections requiring hospitalization
- occurrence and date of hypocalcemia (defined as corrected serum calcium below the age-appropriate lower limit of normal range), and categorically < 9.0 mg/dL

Approved

(patients 0 to < 2 years), < 8.4 mg/dL (patients 2 to 6 years), < 8.0 mg/dL, < 7.5 mg/dL, and < 7.0 mg/dL among subjects who are treated with or without cinacalcet

- occurrence and date of hypocalcemia (as defined by investigator) requiring treatment and action(s) taken

